Clarification of Inclusion #3 that subjects scheduled to undergo a permitted elective procedure who will require a platelet transfusion unless there is a clinically significant change to platelet count from baseline	Clarification	Synopsis – 
 • Inclusion Criteria Section 9.3.1
Revised the exclusion around hemoglobin changing the upper limit from 16 to 17 g/dL and removed the white blood cell count and serum sodium levels exclusion criteria. Subjects who screen failed previously will be permitted to rescreen due to removal of this criteria.	Based upon feedback received from the KOL that these criteria are in contradiction with the requirement for platelet count <math><50 \times 10^9/L</math> (ie, subjects meeting such lab criteria would be relatively too healthy to present with such a low platelet count). Other existing criteria (eg, MELD score and BCLC) will ensure subjects are not too compromised. This also provides for a more diverse population by dropping these restrictions.	Synopsis – 
 • Exclusion Criteria Section 9.1.1.1 Section 9.3.2
Addition of eltrombopag and romiplostim as prohibited	As eltrombopag and romiplostim are used off-label for this indication, both approved	Synopsis – 
 • Prohibited Concomitant Therapy

Revisions to V4.0: 12 Nov 2013 (Amendment 01) Date: V5.0: 22 June 2015 (Amendment 02)		
Change	Rationale	Affected Protocol Sections
medication	thrombopoietin receptor agonists were added	Section 9.4.7.3
Added an evaluation for platelet aggregation to be measured at selected sites	Japan's Pharmaceuticals and Medical Devices Agency (PMDA) requires exploratory assessment of platelet aggregation as part of the platelet function study.	Synopsis – 
 • Safety Assessments Section 9.5.1.5, • Table 4, Table 5 Section 11.3
Updated study director and medical monitor information	Change in Eisai staffing	Protocol Signature Page
Clarified in the appendix the fasting glucose laboratory result should only be considered a treatment-emergent significant abnormality if the result is within normal limits at baseline and has increased in severity to meet the sponsor's grading criteria for laboratory values of Grade 3 or above when fasting.	Clarification	Appendix 2

Revisions to previous V3.0, 29 Sep 2013		
Date: V4.0 (Amendment 01): 12 Nov 2013		
Change	Rationale	Affected Protocol Sections

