Study E5501-G000-202 evaluated the efficacy, safety, and population PK of once-daily oral avatrombopag dosing, in subjects with chronic liver diseases and thrombocytopenia prior to elective surgical or diagnostic procedures. The primary efficacy endpoint was the proportion of responders with platelet count increases from baseline of $\geq 20 \times 10^9/L$ and a platelet count of $\geq 50 \times 10^9/L$ once from Day 4 through Day 8. The proportion of responders for all avatrombopag-treated subjects was 48.4% compared with 8.1% in the combined placebo group ($P < 0.0001$). All doses of avatrombopag achieved a significantly higher proportion of responders compared with their respective cohort placebo arms and the highest platelet count responses were observed between Days 10 to 14 after first dose. In addition, avatrombopag appeared well tolerated in this patient population. There was no clear trend regarding the incidences of AEs between placebo and avatrombopag treatment groups, and the commonly reported treatment-emergent adverse events (TEAEs) and serious TEAEs were consistent with the disease state of the patient population. The findings from Study E5501-G000-202 suggest that avatrombopag would be an effective therapy for the treatment of thrombocytopenia in patients with chronic liver disease, prior to an elective procedure.

For more detailed information regarding effects in humans, please refer to the Investigator Brochure.

7.1.2.4 Common Serious Adverse Events Expected to Occur in the Study Population Even in the Absence of Study Drug Exposure

Thrombotic/thromboembolic complications may occur in patients with chronic liver disease. Portal vein thrombosis (PVT) is of particular concern in chronic liver disease patients who are prone this type of thrombosis and is often associated with poor portal vein flow. The presence of thrombocytopenia can increase the potential for bleeding, which results in an elevated morbidity and mortality risk in patients with liver disease. In cirrhotic patients undergoing abdominal surgery, bleeding accounts for up to 60% of all causes of death. Thrombocytopenic patients often require multiple platelet transfusions, which can be associated with complications such as systemic infections, iron overload, and platelet refractoriness.⁴

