9.3.2 Exclusion Criteria (revised per Amendment 02)

Subjects who meet any of the following criteria will be excluded from this study:

1. Any history of arterial or venous thrombosis, including partial or complete thrombosis
2. Evidence of thrombosis (partial or complete) in the main portal vein, portal vein branches, or any part of the splenic mesenteric system at Screening
3. Portal vein blood flow velocity rate <10 cm/second at Screening
4. Hepatic encephalopathy that cannot be effectively treated
5. Subjects with HCC and Barcelona Clinic Liver Cancer (BCLC) staging classification C or D
6. Platelet transfusion or receipt of blood products containing platelets within 7 days of Screening. However packed red blood cells are permitted
7. Heparin, warfarin, nonsteroidal anti-inflammatory drugs (NSAID), aspirin, verapamil, and antiplatelet therapy with ticlopidine or glycoprotein IIb/IIIa antagonists (eg, tirofiban) within 7 days of Screening
8. Use of erythropoietin stimulating agents within 7 days of Screening
9. Interferon (IFN) use within 14 days of Screening
10. Estrogen-containing hormonal contraceptive or hormone replacement therapy use within 30 days of Screening
11. Active infection requiring systemic antibiotic therapy within 7 days of Screening. However, prophylactic use of antibiotics is permitted.
12. Alcohol abuse, alcohol dependence syndrome, drug abuse, or drug dependence within 6 months of the study start (unless participating in a controlled rehabilitation program) or acute alcoholic hepatitis (chronic alcoholic hepatitis is allowed) within 6 months of the study start
13. Elective procedure performed prior to Visit 4 (Procedure Day)
14. Known to be human immunodeficiency virus (HIV) positive
15. Any clinically significant acute or active bleeding (gastrointestinal, central nervous system, etc.)

16. Known history of any primary hematologic disorder (eg, ITP, myelodysplastic syndrome, etc.)
17. Known medical history of genetic prothrombotic syndromes (eg, Factor V Leiden; prothrombin G20210A; ATIII deficiency etc.) (revised per Amendment 01)
18. Subjects with a history of significant cardiovascular disease (eg, congestive heart failure New York Heart Association Grade III/IV, arrhythmia known to increase the risk of thromboembolic events [eg, atrial fibrillation], coronary artery stent placement, angioplasty, and coronary artery bypass graft [CABG])

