19. Females of childbearing potential who have had unprotected sexual intercourse within 30 days before study entry and who do not agree to use a highly effective method of contraception (eg, total abstinence, an intrauterine device, a double-barrier method [such as condom plus diaphragm with spermicide], a progesterone-only contraceptive implant/injection, or have a vasectomized partner with confirmed azoospermia) throughout the entire study period and for 30 days after study drug discontinuation. If currently abstinent, the subject must agree to use a double-barrier method as described above if she becomes sexually active during the study period or for 30 days after study drug discontinuation. All females will be considered to be of childbearing potential unless they are postmenopausal (at least 12 months consecutive amenorrhea in the appropriate age group and without other known or suspected cause) or have been sterilized surgically (ie, bilateral tubal ligation, hysterectomy, or bilateral oophorectomy) at least 1 month before dosing.
20. Females who are lactating or pregnant at Screening or Baseline (as documented by a positive serum beta-human chorionic gonadotropin [β -hCG] test with a minimum sensitivity 25 IU/L or equivalent units of β -hCG). A separate baseline assessment is required if a negative screening pregnancy test was obtained more than 72 hours before the first dose of study drug.
21. Post liver transplant subjects
22. Any subject who has previously received avatrombopag
23. Hypersensitivity to avatrombopag maleate or any of its excipients
24. Hemoglobin levels ≤ 8.0 or ≥ 18.0 g/dL for men and > 15 for women at Screening, with hematocrit $\geq 54\%$ for men and $\geq 45\%$ for women
25. Current malignancy including solid tumors and hematologic malignancies (except HCC)
26. Any history of concomitant medical condition that, in the opinion of the investigator(s), would compromise the subject's ability to safely complete the study

27. Currently enrolled in another clinical trial with any investigational drug or device within 30 days of Screening

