9.4.7.1 Permitted Prior Therapy

Subjects who have taken IFN previously, but who have discontinued use for at least 14 days before Screening, are eligible for this study. Subjects who have taken erythropoietin-stimulating agents, but who have discontinued use for at least 7 days before Screening, are eligible for this study. Subjects who have taken heparin, warfarin, NSAIDs, aspirin, verapamil, or antiplatelet therapy with ticlopidine or glycoprotein IIb/IIIa antagonists (eg, tirofiban), but who have discontinued use for at least 7 days before Screening, are eligible for this study. Subjects who are taking inhibitors of P-gp (excluding verapamil) and are on a stable dose for at least 7 days before Screening are eligible for this study. Subjects who have received platelet transfusion or blood products containing platelets, but who have had their last treatment at least 7 days prior to Screening, are eligible for this study; however packed red blood cells are permitted throughout.

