9.4.7.3 Prohibited Concomitant Therapy

Erythropoietin stimulating agents are prohibited throughout the study. Interferon use is prohibited during the study; however, at the investigator's discretion, subjects may restart IFN therapy if clinically indicated during the Follow-up Phase (ie, after Visit 4 [Procedure Day]).

Eltrombopag, romiplostim, heparin, warfarin, NSAIDs, aspirin, verapamil, estrogen, and antiplatelet therapy with ticlopidine or glycoprotein IIb/IIIa antagonists (eg, tirofiban) are prohibited. (revised per Amendment 02) Aspirin, for antiplatelet therapy, can be prescribed at the discretion of the investigator in subjects in which the platelet count rises and who are believed to have an increased risk of thrombosis. In subjects where use of aspirin is contraindicated, an alternate antiplatelet therapy such as a platelet adenosine diphosphate receptor inhibitor (eg, clopidogrel) can be prescribed. It should be noted that clopidogrel should be used with due consideration in subjects with liver disease. Lack of activation due to liver disease could lead to a reduction in activation of the prodrug. In addition, as clopidogrel is activated by the CYP system, care is required when administering clopidogrel to subjects with liver disease and co-administering clopidogrel with agents that are substrates or inhibitors of CYP.

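### Eltrombopag and romiplostim are prohibited during the study, but no entry criterion or washout covers their use before Screening (minor; moderate confidence)

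*Protocol*

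**What the plan says.** **Prohibition.** Protocol 9.4.7.3 states: "Eltrombopag, romiplostim, heparin, warfarin, NSAIDs, aspirin, verapamil, estrogen, and antiplatelet therapy with ticlopidine or glycoprotein IIb/IIIa antagonists (eg, tirofiban) are prohibited". The synopsis says the same. No period before Screening is attached. The revision history for Amendment 02 gives the reason: "As eltrombopag and romiplostim are used off-label for this indication".

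**Entry criteria.** Criterion 7 in 9.3.2 reads "Heparin, warfarin, nonsteroidal anti-inflammatory drugs (NSAID), aspirin, verapamil, and antiplatelet therapy with ticlopidine or glycoprotein IIb/IIIa antagonists (eg, tirofiban) within 7 days of Screening". Criteria 8, 9 and 10 cover erythropoietin stimulating agents (7 days), interferon (14 days) and estrogen (30 days). Criterion 22 covers the study drug only: "Any subject who has previously received avatrombopag". No inclusion or exclusion criterion, in the synopsis or the body, names eltrombopag, romiplostim or their class.

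**Permitted prior therapy.** Section 9.4.7.1 gives discontinuation periods for interferon, erythropoietin stimulating agents, platelet products and a group that begins "Subjects who have taken heparin, warfarin, NSAIDs, aspirin, verapamil, or antiplatelet therapy with ticlopidine or glycoprotein IIb/IIIa antagonists". The two agonists are not mentioned.

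**Analysis sets.** SAP 5.2.1 removes subjects from the Per Protocol set for prohibited prior medication, but no section lists which prior medications are prohibited. The primary analysis uses the Full Analysis Set, meaning all randomised subjects. Under 9.4.7, medication taken within 30 days before Visit 1 is recorded on the CRF.

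**The concern.** The two drugs left without an entry window share the study drug's target. A remaining effect would act on platelet count, and so on the primary endpoint and both secondary endpoints. In the placebo arm it could spare a subject a transfusion and narrow the treatment difference. In the avatrombopag arm it could add to the study drug.

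The second possibility sits badly with the protocol's own risk mitigation. Section 7.2.1 reports that 26% of eltrombopag-treated subjects in an earlier trial exceeded 200 × 10⁹/L, and that portal venous thrombosis occurred in 4% on eltrombopag against 1% on placebo. Avatrombopag dosing was chosen so that the projected share above 200 stays below 2%.

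The gap looks like an oversight. Amendment 02 revised both the exclusion list and the prohibited-therapy text, and it recognised off-label use in this population, yet it added the drugs only to the prohibited-therapy text.

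**Working it through.** **1. Prohibited agents against entry windows**

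| Agent prohibited in 9.4.7.3 | Entry window in 9.3.2 | Named in 9.4.7.1 |
|---|---|---|
| Heparin, warfarin, NSAIDs, aspirin, verapamil, ticlopidine, IIb/IIIa antagonists | 7 days (criterion 7) | Yes |
| Erythropoietin stimulating agents | 7 days (criterion 8) | Yes |
| Interferon | 14 days (criterion 9) | Yes |
| Estrogen | 30 days (criterion 10) | No |
| Eltrombopag, romiplostim | None | No |

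Only the last row has no entry window.

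**2. Do other criteria close the gap?** In part.
- Criterion 16, "Known history of any primary hematologic disorder (eg, ITP, myelodysplastic syndrome, etc", removes ITP, an approved use of both drugs (7.1.1). It does not remove off-label users, or users under the US hepatitis C approval of eltrombopag noted in the same section.
- Criterion 27, "Currently enrolled in another clinical trial with any investigational drug or device within 30 days of Screening", concerns trial participation, not marketed product.
- The platelet rule (mean below 50, neither count above 60 × 10⁹/L) removes subjects whose counts are already raised. It cannot remove someone whose rise is still to come, and the two counts need be only one day apart.

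**3. The plan's own power.** Inputs from Protocol 9.7.2: 67 against 33 subjects per cohort, 18% placebo response, a 35-point difference (so 53% on avatrombopag), Fisher's exact test, two-sided 0.05. Exact enumeration over both binomial distributions gives 92.6%, which agrees with the stated figure of more than 90%.

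**4. Power under an assumed residual effect.** Let c be the share of subjects in each arm with a residual effect. The documents give no value for c, so 2%, 5% and 10% are assumptions. Affected placebo subjects are assumed to respond at 53%:

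placebo rate = 0.18(1 − c) + 0.53c

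For avatrombopag there are two limiting assumptions. Either affected subjects gain nothing (rate stays 0.53), or they gain the same 35 points, to 0.88:

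avatrombopag rate = 0.53(1 − c) + 0.88c

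| c | Placebo rate | Power, placebo-only gain | Avatrombopag rate, equal gain | Power, equal gain |
|---|---|---|---|---|
| 0 | 18.0% | 92.6% | 53.0% | 92.6% |
| 2% | 18.7% | 91.3% | 53.7% | 92.3% |
| 5% | 19.75% | 89.0% | 54.75% | 91.7% |
| 10% | 21.5% | 84.4% | 56.5% | 91.0% |

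Under equal gain the difference stays at 35 points, and power slips only because both rates move towards 50%. Under placebo-only gain the difference shrinks to 33.25 points (c = 5%) or 31.5 points (c = 10%).

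**The case against.** The strongest reply is that nothing shows the gap to be material.

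- **Timing.** The only timing evidence is that "the highest platelet count responses were observed between Days 10 to 14 after first dose", which describes avatrombopag in Phase 2. The documents give no onset or duration of action for eltrombopag or romiplostim. A reader might infer that subjects will enter with a rival agonist still acting. The documents support this only as a possibility.
- **When use could occur.** A reader might infer that these drugs can be taken until the day before study drug. Screening is part of the study, and the prohibition is not confined to the time after dosing, so the natural reading covers use from Visit 1. Use continuing at first dose is concomitant by definition (9.7.1.5) and falls under the protocol's Per Protocol rule on prohibited concomitant medication. The gap is use before Screening.
- **Cancelled procedures.** A reader might picture a patient treated with eltrombopag for a procedure later cancelled. On the avatrombopag timing, that patient's count would probably be at or past its peak at entry, where the platelet rule removes responders. The rescreening rule in 9.1.1.1 says nothing about rival agonists.
- **Counts above 200.** A reader might note that 3 of 133 avatrombopag subjects (2.3%) would pass the 2% figure. That figure is a dose-selection projection, and at a true rate of exactly 2% three or more of 133 occur with probability 0.50 without any carry-over. The count shows nothing about prior agonists.
- **Power.** Randomisation balances prior use in expectation, and equal gain keeps power above 90% for c up to 10%.
- **Lateness.** The Amendment 04 rationale says enrolment is already adequate.

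All of this limits the size of the problem. It leaves the mismatch between the entry criteria and the prohibition in place.

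**Conclusion.** The inconsistency is present in the current synopsis and body. Two prohibited agents with the study drug's mechanism lack the entry window that every other agent on the list has, and the SAP's Per Protocol rule has no list that would bring them in.

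The consequence is plausible but unquantified. For an assumed share of 5% to 10%, per-cohort power runs from about 91–92% (equal gain) to 89.0% or 84.4% (placebo-only gain), against 92.6% planned. The true share is unknown and may be small. The expected effect is some dilution and noise, with chance imbalance possible among about 33 placebo subjects per cohort. The documents do not support a claim of directional bias or of a material threat to the primary result. Severity is minor and confidence moderate.

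**What to change.** 1. Reconcile 9.3.2, 9.4.7.1, 9.4.7.3 and the synopsis by adding prior use of eltrombopag, romiplostim or another TPO-receptor agonist to the entry exclusions. The sponsor should set the window.
2. Name these agents in the prohibited-prior-medication criterion of SAP 5.2.1.
3. For subjects already enrolled, identify prior users from the 30-day prior-medication record before database lock and exclude them from the Per Protocol sensitivity analysis. The Full Analysis Set stays as randomised.

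With enrolment nearly complete, steps 2 and 3 matter most. The cost is a few lines of text and a review of data already collected. The downside is a few candidates deferred or excluded and a slightly smaller Per Protocol set. The record reaches back only 30 days before Visit 1, so earlier use would not be found this way.

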9.3.1 Inclusion Criteria

Subjects must meet all of the following criteria to be included in this study:

1. Subjects ≥ 18 years of age at Screening with chronic liver disease
2. Subjects who have a mean baseline platelet count of $< 50 \times 10^9/L$. Platelet counts must be measured on 2 separate occasions, during the Screening Period and at Baseline, and must be performed at least 1 day apart with neither platelet count $> 60 \times 10^9/L$. The mean of these 2 platelet counts (mean baseline platelet count) will be used for entry criteria and for assignment to the low or high baseline platelet count cohort.
3. Subjects scheduled to undergo a permitted elective procedure and who, in the opinion of the investigator, will otherwise require a platelet transfusion to address a risk of bleeding associated with the procedure unless there is a clinically significant increase in platelet count from baseline (revised per Amendments 02 and 03)
4. Model For End-stage Liver Disease (MELD) score ≤ 24 at Screening
5. If taking inhibitors of P glycoprotein (P-gp), except for verapamil, dose must be stable for 7 days prior to Screening (see [Appendix 2](#) for the list of P-gp Inhibitors)
6. Provide written informed consent
7. Willing and able to comply with all aspects of the protocol

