- b: Visit 4 (Procedure Day) assessments will also occur when any subject has been withdrawn or discontinued early from the study for any reason.
- c: Visit 6 (Day 35) assessments will also occur when any subject has been withdrawn or discontinued early from the study for any reason.
- d: BCLC grade is only for subjects with hepatocellular carcinoma.
- e: Comprehensive physical examination at Screening and targeted physical examination at all subsequent visits.
- f: Height will be recorded at Screening (Visit 1) only.
- g: Hematology must be taken prior to any platelet transfusion
- h: Independent platelet counts performed by a local laboratory at Screening and Baseline must be at least 1 day apart with neither platelet count $>60 \times 10^9/L$. The mean of these 2 platelet counts (mean baseline platelet count) must be $<50 \times 10^9/L$ (as per Inclusion Criterion #2), to be eligible to participate in the study.
- i: Complete urinalysis will be performed at Screening and dipstick analysis at all subsequent visits. If urine dipstick is abnormal, a complete urinalysis will be required. After the Screening measurement, fractionation will only be analyzed by the central laboratory in the event CPK level is abnormal.
- j: For females of childbearing potential or who have been amenorrheic for less than 12 months. Serum beta-human chorionic gonadotropin pregnancy testing will be performed at Screening (Visit 1). Urine pregnancy testing will be performed at Visits 2, 4, and 6.
- k: Portal vein flow velocity will be assessed at this visit. Subjects will be required to have a main portal vein blood flow velocity rate of ≥ 10 cm/second at Screening to be eligible for the study.
Three main portal vein blood flow velocity measurements, lasting no less than 4 seconds, will be recorded, and the mean of the 3 values recorded as the final reading.
The Doppler sonography and flow rate assessment can be completed at any time during the Screening Period with results available prior to randomization.
- l: Only subjects whose preprocedural platelet count exceeds $200 \times 10^9/L$ will be required to have a Doppler assessment at Visit 5. For any subjects where the presence of a portal vein thrombosis (PVT) is suspected, confirmation of diagnosis via computerized tomography scan or magnetic resonance imaging, should be performed and treatment for PVT initiated per local guidelines.

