9.5.4.2 Reporting of Pregnancy and Exposure to Study Drug Through Breastfeeding

Any pregnancy in which the estimated date of conception is either before the last visit or within 30 days of last study treatment, or any exposure to study drug through breastfeeding during study treatment or within 30 days of last study treatment, must be reported.

If an adverse outcome of a pregnancy is suspected to be related to study drug exposure, this should be reported regardless of the length of time that has passed since the exposure to study treatment.

A congenital anomaly, death during perinatal period, an induced abortion, or a spontaneous abortion are considered to be an SAE and should be reported in the same time frame and in the same format as all other SAEs (see Reporting of Serious Adverse Events [[Section 9.5.4.1](#)]).

Pregnancies or exposure to study drug through breastfeeding must be reported by fax or email as soon as possible but no later than 1 business day from the date the investigator becomes aware of the pregnancy. The contact information for the reporting of pregnancies and exposure to study drug through breastfeeding is provided in the Investigator Study File. The Pregnancy Report Form must be used for reporting. All pregnancies must be followed to outcome. The outcome of the pregnancy must be reported as soon as possible but no later than 1 business day from the date the investigator becomes aware of the outcome.

A subject who becomes pregnant must be withdrawn from the study.

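### Exclusion criterion 19, read literally, lets in a sexually active woman of childbearing potential who had only protected intercourse in the prior 30 days and declines study contraception (minor wording error)

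*Protocol*

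**What the plan says.** Protocol 9.3.2 excludes a subject who meets any one of its numbered criteria. The first sentence of criterion 19 concerns "Females of childbearing potential who have had unprotected sexual intercourse within 30 days before study entry and who do not agree to use"; what must be agreed to is highly effective contraception. It gives examples of acceptable methods and sets the period as "throughout the entire study period and for 30 days after study drug discontinuation". The second sentence reads: "If currently abstinent, the subject must agree to use a double-barrier method as described above if she becomes sexually active" during that period. The rest of the criterion defines childbearing potential. The Synopsis repeats the first sentence with the same conjunction.

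Other provisions on the subject:

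- Criterion 10 excludes "Estrogen-containing hormonal contraceptive or hormone replacement therapy use within 30 days of Screening".
- Inclusion 7 (9.3.1) requires subjects to be "Willing and able to comply with all aspects of the protocol".
- Criterion 20 excludes women who are pregnant or lactating at Screening or Baseline, and adds: "A separate baseline assessment is required if a negative screening pregnancy test was obtained more than 72 hours before the first dose".
- Table 5, footnote j (9.5.2.1), after a serum test at Screening: "Urine pregnancy testing will be performed at Visits 2, 4, and 6".
- Section 9.5.4.2: "A subject who becomes pregnant must be withdrawn from the study".

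**The concern.** The evident purpose of criterion 19 is that every woman of childbearing potential agrees to effective contraception for the study and for a month after dosing. Joining past behaviour to future agreement with *and* makes refusal grounds for exclusion only when there was also recent unprotected intercourse. A woman who used protection before entry but will not commit to it during the study therefore passes.

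This is an operative eligibility rule on a subject-safety point. Section 11.2 asks investigators to follow the protocol strictly, and 80 to 100 sites are planned. Sites that read the sentence literally and sites that read it for its intent could reach opposite decisions about the same woman.

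**Working it through.** No numerical figure in the plan depends on this point, so the check is one of logic.

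**Step 1. The rule as written and two possible rewrites.** Let U mean unprotected intercourse in the 30 days before entry, and D mean that the woman does not agree to highly effective contraception.

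| U | D | As written (U and D) | Refusal alone (D) | U or D |
|---|---|---|---|---|
| yes | yes | excluded | excluded | excluded |
| yes | no | not excluded | not excluded | excluded |
| no | yes | **not excluded** | excluded | excluded |
| no | no | not excluded | not excluded | not excluded |

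The third row is the gap. Making refusal sufficient changes that row only. Replacing *and* with *or* also changes the second row.

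**Step 2. Does the second sentence of criterion 19 close the gap?** No. It applies only to a woman who is currently abstinent, and the woman in question is sexually active. It does show intent: agreement is asked even of women with no current exposure.

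**Step 3. Does the meaning of *unprotected* matter?** Not to whether the gap exists. If the word means without any protection, the gap covers anyone who used some method before entry and refuses study contraception. If it means without one of the listed methods, the gap still covers a woman who used a listed method and will not agree to continue it. The reading does change how many women are affected.

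**Step 4. Does another provision supply the duty?**

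- The lead-in to 9.3.2 works between numbered criteria. It does not separate the two conditions inside criterion 19.
- Inclusion 7 requires compliance with the protocol, but the protocol states no contraception duty for this woman to comply with.
- Criterion 20 and the tests detect pregnancy. After the Visit 2 test on Day 1, the next is at Visit 4 (Day 10, up to Day 13), after the 5 days of dosing have ended.
- Withdrawal on pregnancy acts only after conception.

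**Step 5. Extent.** Criterion 10 already removes women with estrogen-containing contraceptive use within 30 days of Screening, so the gap concerns users of other methods. The contraception period has two parts. With the last dose on Day 5, 30 days afterwards is Day 5 + 30 = Day 35. Visit 6 is Day 35 with a 3-day allowance, so the study-period part can run to Day 35 + 3 = Day 38. The documents give no count or proportion of women affected.

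**The case against.** The strongest reply is that criterion 19 taken as a whole has one sensible meaning. It lists methods, fixes a period, binds even abstinent women and defines childbearing potential for all females, so most sites would refuse a woman who declines contraception. Failing to meet an exclusion does not oblige a site to enroll, an investigator could lean on inclusion 7, and 9.3.3 allows withdrawal for safety at any time. Under the narrower reading of *unprotected*, the affected group would be women already using a listed method who will not agree to continue it. Several of those methods carry on without any new act, so that group could be close to empty. Exposure is limited too: treatment is short, testing is scheduled, and 7.1.2.2 reports no reproductive toxicity apart from greater sensitivity in neonatal and juvenile rats.

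All of this stands as an argument about weight, and it is why the point is minor. It does not remove the gap. Discretion to refuse is not a rule requiring refusal, and no provision in the available text requires contraception of this woman. The consent form was not available for review. If it contains such a duty, the practical risk is smaller still, but the eligibility criterion would still be misworded.

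**Conclusion.** The concern holds, at minor severity. As written, criterion 19 fails to exclude a sexually active woman of childbearing potential who had only protected intercourse in the previous 30 days and refuses study contraception. This follows from the wording alone and needs no assumption about how *unprotected* is read. The statement that no other provision sets the duty is limited to the protocol text available.

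The number of women affected cannot be calculated and is probably small. The testing and withdrawal rules limit exposure but do not prevent conception. Endpoints, type I error, power and analysis are unaffected. This is best treated as a drafting error in a safety criterion; it does not demonstrate that any subject was harmed.

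**What to change.** In 9.3.2 and the Synopsis, reword the first sentence of criterion 19 so that it excludes any female of childbearing potential who does not agree to a highly effective method, with the list of methods and the period unchanged. Keep the sentence on currently abstinent women. If the sponsor also wants a rule on unprotected intercourse in the 30 days before entry, state it as a separate sentence with its own consequence. Do not simply replace *and* with *or*.

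The edit is one sentence in two places, but it needs a written amendment. Because it concerns subject safety, 11.1 calls for submission to regulatory authorities and IRB/IEC approval at all sites. The Amendment 04 rationale describes enrollment as already adequate, so the change would reach only subjects not yet randomized. It could reasonably be carried in the next amendment, if there is one, instead of a stand-alone amendment.
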